was a significant difference in severity of hypothermia when it did occur.¹³ This study focused only on men undergoing transurethral resection of the prostate however, and suffers from lack of generalizability. With the proportion of the geriatric population continuing to expand, and the potential adverse effects resulting from their increased susceptibility to intraoperative hypothermia, it is of the utmost importance to look into methods to counter this dilemma and expand the database on the topic.

Study Design:

This will be a prospective randomized clinical trial performed at a single academic hospital. Due to the nature of the trial, the anesthesiologists and subjects will not be blinded to their group assignment, but the postoperative assessments will be. All subjects will receive standardized pre-operative preparations, induction, and intraoperative infusions, as dictated by the TIGER anesthesia perioperative protocol.

In addition to these measures, one group will undergo convective warming during the preoperative preparations, completed for a minimum of 60 minutes prior to entering the operating room, while the other group will undergo standard of care, which includes providing each patient with a warming gown that is not turned on as well as blankets and sheets with more blankets provided on patient request.

Study Procedures:

- I. Patient population: 40 patients undergoing gastrointestinal or genitourinary surgeries, who are enrolled in the TIGER anesthesia perioperative protocol
- II. Inclusion criteria:
 - a. ASA I-IV
 - b. Other inclusion criteria as delineated in the TIGER anesthesia perioperative protocol
- III. Exclusion criteria:
 - a. Inability to obtain written informed consent
 - b. Inability to obtain Foley catheter temperature recordings
 - c. Family history of malignant hyperthermia
 - d. Preoperative temperature $> 38^{\circ} \text{ C}$
 - e. Other exclusion criteria as delineated in the TIGER anesthesia perioperative protocol
- IV. Randomization: On the day of surgery, patients will be randomized to one of two groups:
 1. Warming group: This group will undergo pre-warming at a temperature of 43° C or a minimum of 60 minutes beginning upon arrival to the pre-operative room continuing until they are taken to the operating room. This will be achieved with blankets as well as the use of a Bair Hugger® heating gown.

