 2. Standard of care group: this group will receive the standard of care during the preoperative period, which includes providing the patient with blankets and sheets, as well as additional blankets upon request. They will also wear a Bair Hugger® heating gown, but it will not be used for preheating prior to surgery.

V. Randomization will be stratified for the type of surgery (gastrointestinal versus genitourinary) in an effort to reduce confounding.

VI. Blinding: Due to the nature of this study, the anesthesiologist, nursing staff, operating room staff, and the subject will know to which group the subject has been assigned.

VII. Anesthetic management as outlined in the enhanced recovery protocol.

VIII. Postoperative pain management as outlined in the enhanced recovery protocol.

IX. Perioperative assessments

- a. Duration of pre-warming prior to surgery
- b. Temperature change from arrival in the pre-operative holding area to leaving for the operating room as measured by a skin-temperature thermometer.
- c. Temperature change, as measured by a Foley catheter sensor inserted, after induction of anesthesia to the end of surgical skin preparation.
- d. Temperature as measured with a Foley catheter sensor throughout the operative procedure.
- e. Temperature change between leaving the operating room and arrival in the Post Anesthesia Care Unit (PACU).
- f. Duration of hospital stay, estimated blood loss, transfusion requirements, and postoperative complications

X. Sample size and statistical consideration:

- a. This is a pilot study and, if pre-warming is successful at preventing intraoperative hypothermia, data from this study will be used to develop larger studies. We plan to enroll 20 patients per group for a total sample size of 40 subjects to obtain pilot data.
- b. Data will be analyzed using chi-square and t-tests as appropriate with $p < 0.05$ considered significant.

Risks:

- I. No adverse effects are currently expected through participation in this study other than possible sweating and discomfort in patients in the pre-warming group heated for more than one hour.
 - a. Patients in the pre-warming group will be warned of the potential for sweating or discomfort due to warmth during informed consent at the pre-operative clinic visit. If they feel uncomfortable during the pre-warming process, staff will turn down the warmers from 43C to 38C; if symptoms persist staff will turn the warmers off.

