 - b. If significant adverse events other than sweating or discomfort occur, the gown will be turned off, standard of care for the event provided, and the investigators will be notified
- II. All identifiable information will be kept in a secure location and will not be given to anyone unaffiliated with the University Hospital except as required by law.
 - a. Despite efforts to maintain confidentiality, a small risk associated with breach of confidentiality is still present
- III. There are no anticipated financial risks to patients.

Benefits:

Direct Benefit -

- In the pre-warming group, patient's may feel warmer pre- and post-operatively. Patients may also have higher temperatures throughout the day of surgery which may contribute to decreased incidence of hypothermia and its adverse effects.

Indirect Benefit -

- Patients may benefit from taking part in this research to the extent that they are contributing to medical knowledge. The information learned from this study may benefit other patients with risk of low body temperatures during surgery in the future.

Costs:

Patients will be required to pay for any treatment considered standard of care for the procedure under which they will be going. Bair Hugger® gowns are included in standard of care measures (each patient is provided with one pre-operatively whether or not they are used) and thus using them throughout the morning, prior to surgery, does not increase cost.

Ethical Considerations:

- I. Patient Expectations:
 - a. This study is not double-blinded and thus patients in the experimental arm may expect improved outcomes due to participation.
 - b. Expectations of improved outcomes will be managed in the pre-operative clinic setting during the informed consent process.
 - c. Patients will be explicitly told that this trial measures temperatures and only a few post-operative clinical outcomes, thus they may not experience a tangible benefit.
- II. Patient Comfort:
 - a. Increasing pre-operative temperatures with convective heating methods may compromise patient comfort and cause sweating to occur;¹⁴ this will be clearly explained to all patients agreeing to participate in the study during the informed consent process.
 - i. If patients in the experimental arm begin to feel uncomfortable, the staff will lower the temperature of the

heating gown from 43°C to 38°C; if discomfort persists at 38°C, staff can turn the heating gown off

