- b. Patient comfort may be compromised by use of Foley catheter temperature sensors; this will be mitigated by insertion of catheters post-induction.
 - i. Inserting Foley catheters is routine care for all of the surgeries studied in this trial and thus should not be exposing patients to the potential of more harm than is inherent in the process of surgery

III. Confidentiality:

- a. Investigators will have access to patient information and records.
- b. All paper files will be de-identified
- c. All computerized information will be de-identified and kept in files on password-secured computers in the University of Missouri Department of Anesthesiology
- d. A code key with identifiable information will be kept in a separate secure location

IV. Informed Consent:

- a. Informed consent will be obtained from all participating patients in the pre-operative clinic setting.
- b. This study is excluding vulnerable patients comprising of prisoners, minors, and those with mental disability in order to maintain the integrity of the informed consent process.

V. Managing Adverse Events:

- a. No adverse effects are currently expected through participation in this study other than possible sweating and discomfort in patients heated more than one hour.¹⁴
- b. If any adverse events should arise due to pre-warming measures, they will be documented in the patient's chart, disclosed to the PI, and observed in study results.

- c. If any serious adverse events occur due to pre-warming measures, that interfere with or require discontinuation of said measures, patient's will be treated with the standard of care for the event and it will be disclosed to the PI immediately for review of safety.

VI. Retention of Records:

- a. Paper patient records will be retained in a locked cabinet for no more than 7 years after completion of the study.
- b. For retention of computerized patient records, within 1 year of completion of the study they will be printed and held in a locked cabinet for no more than 7 years after completion of the study.

VII. Gender Considerations:

- a. This intervention is expected to affect both male and female patients and is not currently intended for use in only one sex.

References:

1. Centers for Disease Control and Prevention. The State of Aging and Health in America 2013. Atlanta, GA: Centers for Disease Control and Prevention, US Dept of Health and Human Services; 2013.

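### The adverse-event rule covers only events attributed to pre-warming, so events before and during surgery are not collected in both arms and cannot be compared

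*Combined protocol and SAP*

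**What the plan says.** Ethical Considerations, V. Managing Adverse Events, item b: "If any adverse events should arise due to pre-warming measures, they will be documented". The destinations named are the patient's chart, the PI and the study's results. Item c, on serious events, carries the same condition and adds a second: "If any serious adverse events occur due to pre-warming measures, that interfere with or require discontinuation of said measures".

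Risks, I.b has no causality wording: "If significant adverse events other than sweating or discomfort occur, the gown will be turned off, standard of care for the event provided", after which the investigators are told.

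The control arm is described in Study Procedures, IV.2: "They will also wear a Bair Hugger® heating gown, but it will not be used for preheating prior to surgery". On blinding, Study Procedures, VI says that "the anesthesiologist, nursing staff, operating room staff, and the subject will know to which group the subject has been assigned", while the Study Design section says that "the anesthesiologists and subjects will not be blinded to their group assignment, but the postoperative assessments will be".

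Study Procedures, IX lists the perioperative assessments. Item a is the duration of pre-warming, items b to e are temperatures, and item f covers length of stay, blood loss, transfusion and postoperative complications. Sweating and discomfort during heating are the only adverse effects the protocol expects (Risks, I; Ethical Considerations, V.a). It gives no rate for them.

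**The concern.** V.b uses a causal judgement to decide whether an event enters the study record. A judgement of that kind normally follows recording. Control patients have no pre-warming to which an event could be attributed, so their count under V.b is zero whatever happens to them. In the warmed arm the count depends on the true event rate and also on how readily events are attributed. No one is named to make that attribution and no criteria are given.

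Tolerability before and during surgery is at stake. Study Procedures, X.a says that data from this pilot will feed the design of larger studies if warming works. A designer would want to know how often warmed patients sweat or are uncomfortable, compared with patients under blankets in an inactive gown. V.b promises that the events will appear in the results, but the stated rule supplies only one side of that comparison.

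**Working it through.** The plan states no figure on this point, so there is nothing to reproduce. The check has two parts: which events have a recording route, and what a one-sided record does to a comparison.

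**Routes for an adverse event**

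| Route | Condition | Can a control event before or during surgery enter? |
|---|---|---|
| V.b | due to pre-warming | No |
| V.c | serious, due to pre-warming, and interfering with it or requiring that it stop | No |
| Risks I.b | significant, other than sweating or discomfort | No causality condition, but the action fits a gown in use; it gives notification, with no recording step |
| IX.f | none by arm or cause | Only if it shows as blood loss, transfusion, longer stay or a postoperative complication |

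Sweating and discomfort in the holding area fall outside IX.f, and Risks I.b sets them aside by name. In a warmed patient they reach the record through V.b if attributed. In a control patient they have no stated route. A minor event in a warmed patient that is judged unrelated has no route under V.b either. IX.a would partly reflect a gown being switched off, but nothing requires a reduction in setting, or the reason for it, to be recorded.

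**Effect on a between-arm contrast**

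Let p_W and p_C be the true proportions of patients with an event, and a the share of warmed-arm events attributed to warming.

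- Recorded difference = a·p_W − 0
- True difference = p_W − p_C
- Bias = a·p_W − (p_W − p_C) = p_C − (1 − a)·p_W

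With 20 patients per arm (Study Procedures, X.a) and assumed rates:

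- p_W = p_C = 0.20, a = 0.5: expected record 20 × 0.20 × 0.5 = 2 against 0; truth 4 against 4. Bias = 0.20 − 0.10 = +0.10.
- p_W = 0.30, p_C = 0.10, a = 1: recorded difference 0.30, true 0.20. Bias = +0.10.
- p_W = 0.30, p_C = 0.10, a = 0.5: recorded difference 0.15, true 0.20. Bias = 0.10 − 0.15 = −0.05.

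So the bias can go either way, and it depends on a and p_C, neither of which the study would observe.

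**If the counts were tested (illustration only; the plan specifies no adverse-event test)**

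For x/20 against 0/20 the uncorrected chi-square is 40x/(40 − x). At x = 3 it is 120/37 = 3.24 (p = 0.072); at x = 4 it is 160/36 = 4.44 (p = 0.035). Fisher's exact test gives p = 0.106 at x = 4 and first falls below 0.05 at x = 5 (p = 0.047). Assume equal true rates of 10%, 15% or 20% and full attribution. The chance of a false significant difference is then P(X ≥ 4) = 13%, 35% or 59% by chi-square, and P(X ≥ 5) = 4%, 17% or 37% by Fisher. With half attributed, the chi-square figure is 2% at a 10% rate and 13% at 20%. With both arms recorded regardless of cause, chi-square type I error is 3.9% at 10% and 5.0% at 20%.

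If no event were attributed, the warmed arm would show 0/20. Even read at face value, that leaves a two-sided 95% upper limit of 1 − 0.025^(1/20) = 16.8%.

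**The case against.** The strongest reply is that V.b says what happens to attributed events and does not forbid recording others. That is correct. A reader might infer that the control arm has no safety data at all, but IX.f contradicts this. The gap is in events before and during surgery.

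A reader might also infer that unblinded staff decide what counts. The documents name no causality assessor, and they describe postoperative assessments as blinded. They establish only that the perioperative staff know the allocation and that the assessor is unspecified.

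Nor can it be said that a misjudged event is lost to safety review. Risks I.b has investigators notified of significant events with no causality condition. What remains is that a minor event judged unrelated has no recording route under V.b.

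It is also fair to say that sweating and discomfort in a warmed patient are the events most likely to be attributed, so the warmed-arm rate may be largely obtainable. Gown adjustments arise only in that arm, so a control count of them would add nothing. The main loss is the control background rate, together with any assurance that warmed-arm capture is complete.

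Finally, adverse events are not an endpoint, X.b applies tests only as appropriate, and equal true rates are unlikely for heat-related symptoms. The false-significance percentages therefore show the mechanism. They do not forecast this trial's results.

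**Conclusion.** The point holds in a limited form. Under V.b and V.c no control event can qualify. Outside the IX.f outcomes and the notification in Risks I.b, the plan has no both-arm collection of preoperative or intraoperative adverse events. The pilot therefore cannot give an unbiased between-arm comparison of sweating, discomfort or other events in that period.

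This rests on the wording of the rules and needs no assumed rate. The size does need one. Under the assumptions shown, the recorded difference is off by 5 to 10 percentage points, in either direction. The primary endpoint and its analysis are untouched. This is an inexpensive improvement to a pilot, best made before enrolment because unrecorded discomfort may not be recoverable later.

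**What to change.** Reword V.b so that every adverse event from holding-area arrival to PACU discharge is recorded in both arms, on the same form and regardless of cause, with sweating and discomfort included. In the warmed arm, also record any reduction in the gown's setting or switching off, with its time and reason. Make relatedness a separate field completed by a named role, and align V.c with this. Report counts by arm descriptively, without a significance test.

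The change concerns recording only and alters no rule for managing patients. It costs a slightly longer form for 40 patients and a sentence or two of protocol text.
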